9.4.2. Physical Examination

One complete physical examination (excluding pelvic and rectal examinations) will be performed at screening. This examination will determine whether the patient meets the criteria required to participate in the study and will also serve as a monitor for preexisting conditions and as a baseline for TEAE assessment. Body weight and height will also be recorded. Additional limited physical examinations will also be performed during the study (Section 2, Schedule of Activities).

Fundoscopy may be completed as part of the physical examination, as necessary if, in the opinion of the investigator, it is needed to monitor safety in specific AGS patients.

9.4.3. Vital Signs

Vital signs (eg, blood pressure and pulse) will be measured at times indicated in the Schedule of Activities (Section 2). Any clinically significant findings that result in a diagnosis should be captured on the eCRF and reported as an AE. Additional measurements of vital signs may be performed at the discretion of the investigator.

9.4.4. Laboratory Tests

The investigator must review the laboratory report, document this review, and record any clinically relevant changes occurring during the study in the AE section of the eCRF. The laboratory reports must be filed with the source documents. Clinically significant abnormal laboratory findings are those which are not associated with the underlying disease, unless judged by the investigator to be more severe than expected for the patient's condition.

All laboratory tests with values considered clinically significantly abnormal during participation in the study or within 28 days after the last dose of study intervention should be repeated until the values return to normal or baseline or are no longer considered clinically significant by the investigator or medical monitor.

- o If such values do not return to normal/baseline within a period of time judged reasonable by the investigator, the etiology should be identified and the sponsor notified.
- o All protocol-required laboratory assessments, as defined in [Appendix 2](#), must be conducted in accordance with the laboratory manual and the Schedule of Activities (Section 2).
- o If laboratory values from non-protocol- specified laboratory assessments performed at the institution's local laboratory require a change in patient management or are considered clinically significant by the investigator (for example, SAE or AE or dose modification), then the results must be recorded in the eCRF.

For each patient, laboratory tests detailed in ([Appendix 2](#)) should be conducted according to the Schedule of Activities (Section 2). For pediatric patients, reference ranges should be based on the patients' age groups as defined by the central laboratory.

Due to blood volume restrictions and patient conditions, some laboratory tests may not be collected. Use of local anesthetics (eg, eutectic mixture of local anesthetics [EMLA] cream) consistent with local prescribing information is permitted during the study visit to ease discomfort associated with venipunctures. Lilly or its designee will provide the investigator with the results of laboratory tests analyzed by a central vendor, if a central vendor is used for the clinical trial.

Additional blood samples may be drawn if needed for safety purposes and/or if warranted and agreed upon between the investigator and Lilly or its designee.

Blood volume restrictions:

In cases where required blood samples cannot be collected due to blood volume limitations relative to patient size/age, the investigator must consult with the Lilly-designated medical personnel to determine which samples to prioritize. The investigator should also refer to the blood sample prioritization guidance tool which is a supplemental instruction provided by sponsor. When required samples are not collected due to restrictions, this will not be considered a protocol violation, but this will need to be documented in the medical record.

Fasting Laboratory Tests:

Fasting lipid profile: Patients should not eat or drink anything except water for 4 to 12 hours, depending on weight and age, as specified below. If a patient attends these visits in a nonfasting state, this will not be considered a protocol violation. Recommended fasting times by age and weight are as follows:

- Patients ≥ 12 years: fast for 12 hours prior to laboratory sampling;
- Patients 8 to < 12 years and weighing > 50 kg: fast for 12 hours prior to laboratory sampling;
- Patients 8 to < 12 years and weighing ≤ 50 kg: fast for 8 hours prior to laboratory sampling;
- Children < 8 years and weighing 25 to ≤ 50 kg: fast for 8 hours prior to laboratory sampling;
- Children < 8 years and weighing 10 to < 25 kg: fast for 6 hours prior to laboratory sampling; and
- Children < 8 years and weighing < 10 kg: fast for 4 hours prior to laboratory sampling.

Urine Sample Collection:

If a urine sample cannot be collected, in particular, from patients who have not been toilet trained or who have physical impairment caused by primary disease, this will not be considered a protocol violation, provided that the site maintains appropriate documentation of why the sample cannot be collected.

9.4.5. Other Tests

9.4.5.1. Pulmonary Function Monitoring for SAVI Patients

The progression of pulmonary disease will be monitored in an age-based manner in SAVI patients. Monitoring may include vital signs, pulse oximetry, imaging, laboratory tests (eg, KL6) and pulmonary function tests, including diffusing capacity of the lung for carbon monoxide. The contents of monitoring can be modified by the investigator. Pulmonary function monitoring will

be locally performed at any time during the study, including the follow-up period, if medically necessary in the opinion of the investigator.

9.4.5.2. Screening for BK Virus in Blood and Urine

Patients will be tested for the presence of BK virus in blood and urine at baseline (prior to the first dose of baricitinib) and periodically, thereafter, as specified in Section 2. BK virus test may be performed at any time during the study, including the follow-up period, if medically necessary in the opinion of the investigator.

9.4.6. Safety Monitoring

Lilly will periodically review evolving aggregate safety data within the study by appropriate methods.

The Lilly clinical research physician will monitor safety data throughout the course of the study and will, as appropriate, consult with the functionally independent Global Patient Safety therapeutic area physician or clinical scientist.

See Section 8.1 for discontinuation criteria related to specific AEs.

Vitals signs will be monitored as indicated in the Schedule of Activities (Section 2).

9.4.6.1. Hepatitis B Virus DNA Monitoring

Hepatitis B virus DNA testing will be performed in enrolled patients who tested positive for HBcAb or HBsAb at Visit 1 (screening).

Patients who are positive for HBcAb or HBsAb and negative for HBV DNA (undetectable based on central results) at screening will require HBV DNA monitoring at Week 12 (Visit 10), Week 24 (Visit 13), Week 36 (Visit 16), Week 48 (Visit 19), Week 52 (Visit 20), Week 64 (Visit 21), Week 76 (Visit 22), Week 88 (Visit 23), Week 100 (Visit 24), Week 112 (Visit 25), Week 124 (Visit 26), Week 136 (Visit 27), Week 148 (Visit 28), Week 160 (Visit 29), Week 172 (Visit 30), Week 184 (Visit 31), Week 196 (Visit 32), Week 208 (Visit 33), Week 220 (Visit 34), Week 232 (Visit 35), Week 244 (Visit 36), early termination visit (ETV), and the posttreatment follow-up period (V801). As an exception, patients who are HBcAb-negative, HBsAb-positive with a documented history of Hepatitis B vaccination will not be required to undergo HBV DNA testing at Visit 1 nor HBV DNA monitoring throughout the study.

The following actions should be taken in response to HBV DNA test results:

- If a single result is obtained with a value that is below the limit of quantitation, the test should be repeated within approximately 2 weeks. If the repeat test does not detect the target, monitoring will resume according to the schedule of activities.
- If the patient has 2 or more HBV DNA test results with a value that is below the limit of quantitation, HBV DNA testing should be performed approximately once per month for the remainder of the study and referral to a hepatologist is recommended.

- If a result is obtained with a value that is above the limit of quantitation, at any time during the study, the patient will be permanently discontinued from investigational product (Section 8.1.1) and should be referred to a hepatology specialist.
 - In selected cases, investigators may temporarily continue investigational product in accordance with current immunomodulator management in the setting of HBV DNA positivity. This option may be considered in consultation with Lilly (or its designee) and evaluation of individual patient risks and benefits.

Note: Unscheduled visits may be used for monitoring of HBV DNA, when necessary.

Table JAJE.7. Interpretation of HBV Serology at Screening

HBsAg	HBcAb	HBsAb	HBV DNA	Interpretation
Positive	N/A	N/A	N/A	Patients with positive HBsAg are excluded
N/A	N/A	N/A	Detected	Patients with detectable HBV DNA are excluded
Negative	Negative	Negative	Not detected	Eligible for inclusion, provided the patient meets the inclusion criteria and does not meet other exclusion criteria
Negative	Positive	Negative	Not detected	May be eligible for inclusion, provided the patient meets the inclusion criteria and does not meet other exclusion criteria.
Negative	Negative	Positive	Not detected	Monitor HBV DNA periodically as described in the Schedule of Activities (Section 2) 
 • Patients who are anti-HBc-, anti-HBs+ with a documented history of Hepatitis B vaccination will not be required to undergo HBV DNA testing/monitoring.
Negative	Positive	Positive	Not detected	

Abbreviations: anti-HBc = anti-hepatitis B core antibody; anti-HBs = anti-hepatitis B surface antibody; DNA = deoxyribonucleic acid; HBcAb = anti-hepatitis B core antibody; HBsAb = hepatitis B surface antibody; HBsAg = hepatitis B surface antigen; HBV = hepatitis B virus; N/A = not applicable; in these cases, a positive or negative test result.

9.4.6.2. Hepatic Safety Monitoring

9.4.6.2.1. Close hepatic monitoring*

Laboratory tests (Appendix 4), including ALT, AST, ALP, TBL, direct bilirubin (D. Bil), GGT, and creatine kinase (CK), should be repeated within 48 to 72 hours to confirm the abnormality and to determine if it is increasing or decreasing, if one or more of these conditions occur:

If a patient with baseline results of ...	develops the following elevations:
ALT or AST $<1.5 \times$ ULN	ALT or AST $\geq 3 \times$ ULN
ALP $<1.5 \times$ ULN	ALP $\geq 2 \times$ ULN
TBL $<1.5 \times$ ULN	TBL $\geq 2 \times$ ULN (except for patients with Gilbert's syndrome)
ALT or AST $\geq 1.5 \times$ ULN	ALT or AST $\geq 2 \times$ baseline
ALP $\geq 1.5 \times$ ULN	ALP $\geq 2 \times$ baseline
TBL $\geq 1.5 \times$ ULN	TBL $\geq 1.5 \times$ baseline (except for patients with Gilbert's syndrome)

Abbreviations: ALP = alkaline phosphatase; ALT = alanine aminotransferase; AST = aspartate aminotransferase;

TBL = total bilirubin; ULN = upper limit of normal.

* All ULN values should be age adjusted (AAULN)

If the abnormality persists or worsens, clinical and laboratory monitoring, and evaluation for possible causes of abnormal liver tests should be initiated by the investigator in consultation with the Lilly-designated medical monitor. At a minimum, this evaluation should include physical examination and a thorough medical history, including symptoms, recent illnesses (eg, heart failure, systemic infection, hypotension, or seizures), recent travel, history of concomitant medications (including over-the-counter), herbal and dietary supplements, history of alcohol drinking and other substance abuse.

Initially, monitoring of symptoms and hepatic biochemical tests should be done at a frequency of 1 to 3 times weekly, based on the patient's clinical condition and hepatic biochemical tests. Subsequently, the frequency of monitoring may be lowered to once every 1 to 2 weeks, if the patient's clinical condition and lab results stabilize. Monitoring of ALT, AST, ALP, and TBL should continue until levels normalize or return to approximate baseline levels. Special care should be taken for pediatric patients to minimize the volume of blood taken during hepatic monitoring.

9.4.6.2.2. *Comprehensive hepatic evaluation**

A comprehensive evaluation should be performed to search for possible causes of liver injury if one or more of these conditions occur:

If a participant with baseline results of...	develops the following elevations:
ALT or AST <1.5x ULN	ALT or AST \geq 3x ULN with hepatic signs/symptoms**, or ALT or AST \geq 5x ULN
ALP <1.5x ULN	ALP \geq 3x ULN
TBL <1.5x ULN	TBL \geq 2x ULN (except for patients with Gilbert's syndrome)
ALT or AST \geq 1.5x ULN	ALT or AST \geq 2x baseline with hepatic signs/symptoms**, or ALT or AST \geq 3x baseline
ALP \geq 1.5x ULN	ALP \geq 2x baseline
TBL \geq 1.5x ULN	TBL \geq 2x baseline (except for patients with Gilbert's syndrome)

* All ULN values should be age adjusted (AAULN)

** Hepatic signs/symptoms are severe fatigue, nausea, vomiting, right upper quadrant abdominal pain, fever, rash, and/or eosinophilia >5%.

For adult patients (\geq 18 years old)

At a minimum, this evaluation should include physical examination and a thorough medical history, as outlined above, as well as tests for PT-INR; tests for viral hepatitis A, B, C, or E; tests for autoimmune hepatitis; and an abdominal imaging study (for example, ultrasound or CT scan).

Based on the patient's history and initial results, further testing should be considered in consultation with the Lilly-designated medical monitor, including tests for hepatitis D virus (HDV), cytomegalovirus (CMV), Epstein-Barr virus (EBV), acetaminophen levels, acetaminophen protein adducts, urine toxicology screen, Wilson's disease, blood alcohol levels, urinary ethyl glucuronide, and blood phosphatidylethanol. Based on the circumstances and the investigator's assessment of the participant's clinical condition, the investigator should consider referring the participant for a hepatologist or gastroenterologist consultation, magnetic resonance cholangiopancreatography (MRCP), endoscopic retrograde cholangiopancreatography (ERCP), cardiac echocardiogram, or a liver biopsy.

For pediatric patients ($<$ 18 years old)

At a minimum, this evaluation should include physical examination and a thorough medical history, as outlined above, as well as tests for PT-INR and D. Bil, if TBL was elevated.

Based on the participant's age, medical history and initial results, further testing should be considered in consultation with the Lilly-designated medical monitor, including tests for viral hepatitis A, B, C, E; autoimmune hepatitis; or an abdominal imaging study (for example, ultrasound, MRI, or CT scan). Consider additional tests, based on the medical history and clinical picture, including tests for HDV, CMV, EBV, acetaminophen levels, acetaminophen protein adducts, urine toxicology screen, Wilson's disease, blood alcohol levels, urinary ethyl glucuronide, and blood phosphatidylethanol. Special care should be taken to prioritize more

pertinent blood tests and minimize the volume of blood taken during hepatic evaluation. Based on the circumstances and the investigator's assessment of the participant's clinical condition, the investigator should consider referring the participant for a pediatric hepatologist or gastroenterologist consultation, MRCP, ERCP, cardiac echocardiogram, or a liver biopsy as deemed appropriate for the clinical condition and participant's age.

If any of the above specific abnormalities in the section of close hepatic monitoring and comprehensive hepatic evaluation, are considered a feature of the disease (NNS/CANDLE, SAVI, or AGS), the investigator should discuss appropriate monitoring for the patient with Lilly or its designee.

9.4.6.2.3. Hepatic Safety Data Collection

Additional hepatic safety data collection in hepatic safety case report forms (CRF) should be performed in study patients who meet 1 or more of the following 5 conditions: *

- Elevation of serum ALT to $\geq 5 \times$ ULN on 2 or more consecutive blood tests (if baseline ALT $< 1.5 \times$ ULN);
 - In patients with baseline ALT $\geq 1.5 \times$ ULN, the threshold is ALT $\geq 3 \times$ baseline on 2 or more consecutive tests;
- Elevated TBL to $\geq 2 \times$ ULN (if baseline TBL $< 1.5 \times$ ULN) (except for cases of known Gilbert's syndrome);
 - In patients with baseline TBL $\geq 1.5 \times$ ULN, the threshold should be TBL $\geq 2 \times$ baseline;
- Elevation of serum ALP to $\geq 2 \times$ ULN on 2 or more consecutive blood tests (if baseline ALP $< 1.5 \times$ ULN);
 - In patients with baseline ALP $\geq 1.5 \times$ ULN, the threshold is ALP $\geq 2 \times$ baseline on 2 or more consecutive blood tests;
- Hepatic event considered to be an SAE;
- Discontinuation of study drug due to a hepatic event.

Note: the interval between the two consecutive blood tests should be at least 2 days.

* All ULN values should be age adjusted (AAULN)

9.4.7. Growth Monitoring

Height, weight, and occipital frontal circumference measurement (children less than 3 years old) will be measured at pretreatment and posttreatment for the assessment of physical growth according to the Schedule of Activities (Section 2). Height and weight changes in pediatric patients at an individual level will be reviewed by the study medical monitor.

9.5. Pharmacokinetics

Pharmacokinetic samples will be collected from all patients at the time points shown in Table JAJE.8. Pharmacokinetic samples will be used to determine the concentrations of baricitinib using a validated bioanalytical method.

Venous blood samples for the measurement of baricitinib concentrations will be collected from all patients enrolled in the study. At least 72 hours of dosing in a certain dosing regimen is needed before PK samples can be taken.

Table JAJE.8. Pharmacokinetic Sampling

PK sampling visits	PK sampling time points
Visit 7 ^{a,b} and Visit 11 ^{a,b}	Collect the following 4 PK samples in the morning ^c : 
 • Pre-morning-dose • 1 hour post-morning-dose • 1.5 hours post-morning-dose • 4 hours post-morning-dose
Visit 12 ^a	Collect the following 1 PK sample in the morning ^c : 
 • Pre-morning-dose

Abbreviation: PK = pharmacokinetic.

- ^a If PK samples cannot be processed within the specified time after collection, the PK samples may be collected on the next visit.
- ^b In case where the blood volume required exceeds that of tolerable amount for 1 visit, the corresponding PK samples that could not be drawn on that visit can be taken on the next visit. It is also possible for them to be taken over a multiple of visits prior to the next PK-required visit.
- ^c If PK samples are taken at the time points other than morning-dose, this will not be considered a protocol violation.

Additional unscheduled PK samples may be collected with Lilly or its designee approval to assess safety and dosing, and this can be considered especially in patients with eGFR <60 mL/min/1.73 m².

For both scheduled and unscheduled PK samples taken, the actual date and exact timing (24-hour clock) of PK sample collection should be recorded. The date and time of the last 2 doses prior to the PK sample taken should be recorded. In addition, doses taken by the patients during their stay in the clinic on the visits where PK samples were taken should also be recorded.

Pharmacokinetic samples will be kept in storage at a laboratory facility designated by Lilly. Bioanalytical samples collected to measure baricitinib concentration will be retained for a maximum of 1 year following last patient visit for the study.

9.6. Pharmacodynamics

Refer to Section 9.1.2.6.

9.7. Pharmacogenomics

9.7.1. Whole Blood Sample for Pharmacogenetic Research

A whole blood sample will be collected for pharmacogenetic analysis as specified in the Schedule of Activities (Section 2) where local regulations allow.

Samples will not be used to conduct unspecified disease or population genetic research either now or in the future. Samples will be used to investigate variable response to baricitinib and to investigate genetic variants thought to play a role in NNS/CANDLE, SAVI, or AGS.

Assessment of variable response may include evaluation of AEs or differences in efficacy.

All samples will be coded with the patient number. These samples and any data generated can be linked back to the patient only by the investigator site personnel.

Samples will be retained at a facility selected by Lilly or its designee for a maximum of 15 years after the last patient visit for the study, or for a shorter period if local regulations and/or IRBs impose shorter time limits.

Molecular technologies are expected to improve during the 15-year storage period and, therefore, cannot be specifically named. However, existing approaches include whole genome or exome sequencing, genome-wide association studies, and candidate gene studies. Regardless of technology utilized, genotyping data generated will be used only for the specific research scope described in this section.

9.8. Biomarkers

Biomarker research is performed to address questions of relevance to drug disposition, target engagement, pharmacodynamics, mechanism of action, variability of patient response (including safety), and clinical outcome. Sample collection is incorporated into clinical studies to enable examination of these questions through measurement of biomolecules including DNA, RNA, proteins, lipids, and other cellular elements.

Blood samples for nonpharmacogenetic biomarker research will be collected at the times specified in the Schedule of Activities (Section 2). Samples will be used for research on the drug target, disease process, variable response to baricitinib, pathways associated with NNS/CANDLE, SAVI, or AGS, mechanism of action of baricitinib, and/or research method, or to validate diagnostic tools or assay(s) related to these diseases.

All samples will be coded with the patient number. These samples and any data generated can be linked back to the patient only by the investigator or site personnel.

Samples will be retained at a facility selected by Lilly for a maximum of 15 years after the last patient visit, or for a shorter period, if local regulations require. The duration allows Lilly to respond to future regulatory requests related to the investigational product. Any samples remaining after 15 years will be destroyed.

10. Statistical Considerations

10.1. Sample Size Determination

Because the medical conditions being treated in the study are very rare in Japan, it is anticipated that relatively few patients will be enrolled. Approximately 5 patients will be enrolled. The Sponsor will try to enroll more than 1 patient per disease.

However, given the scarcity of patient population for each of these target diseases in Japan, it may be possible that the study is completed without enrolling any patients for a specific disease if no eligible patients could be found.

10.2. Populations for Analyses

For purposes of analysis, the following populations are defined:

Population	Description
Enrolled	All subjects who sign informed consent or assent (as applicable), and meet all eligibility criteria
Full analysis set	All enrolled subjects who take at least 1 dose of study treatment.

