Patients who meet all of the inclusion criteria (Section 6.1) and do not meet any of the exclusion criteria (Section 6.2) may enter the study (that is, sign consent or assent). In addition, patients must meet the enrollment criteria (Section 6.1) in order to be eligible to receive baricitinib.

Prospective approval of protocol violations to recruitment and enrollment criteria, also known as protocol waivers or exemptions, are not permitted.

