6.1. Inclusion Criteria

Patients are eligible for entry into the study only if they meet all of the following criteria at Visit 1 (screening) and Visit 6 (enrollment, baseline) unless otherwise specifically defined:

Type of Patient and Disease Characteristics

- [1] Have systemic signs and symptoms of inflammation as manifested by the presence of 2 or more signs or symptoms as defined in CANDLE/SAVI/AGS diary (investigator must assess patient eligibility using a patient diary related to their disease; see Section 9.1.1.1, 9.1.1.2, and 9.1.1.3)
- [2] Have been diagnosed with NNS/CANDLE, SAVI, or AGS (including FCL) with the confirmation with genetic diagnosis.
- [3] Have the designated daily diary score assessed over the designated period during the screening and pretreatment period. Average daily diary score will be calculated using data from 7 days preceding the current visit (not including data on the day of current visit) (see Section 9.1.1.1)

Average daily diary score at Visit 2 (only for NNS/CANDLE patients) and Visit 6 (for all patients):

- NNS/CANDLE patients: average daily diary score of ≥ 0.5 ,
- SAVI patients: average daily diary score of ≥ 1.0 ,
- AGS patients: average daily diary score of ≥ 0.5 .

Note: SAVI and AGS patients are required to collect daily diary score over at least 7 days prior to Visit 6. If scores are missing and the total number of daily diary score is < 7 days, the eligibility for moving to Visit 6 may be considered after consultation with Lilly or its designee. NNS/CANDLE patients are required to collect daily diary score through 13 weeks according to the screening and pre-treatment period.

If the average daily diary score does not meet the criterion, but the patient's condition warrants appropriate assessment in this study, moving to Visit 6 may be allowed after consultation with Lilly or its designee. The eligibility for moving to Visit 6 will be judged by Lilly or its designee.

Patient Characteristics

[4] are male or female patients:

[4a] Female patients:

Women not of child-bearing potential or nonbreastfeeding:

- 12 months of amenorrhea for women >55 , with no need for FSH
OR

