8.1.3. Discontinuation of Inadvertently Enrolled Patients

If Lilly or investigator identify a patient who did not meet enrollment criteria and was inadvertently enrolled, then the patient should be discontinued from study treatment unless there are extenuating circumstances that make it medically necessary for the patient to continue on study treatment. If the investigator and Lilly or its designee agree it is medically appropriate to continue, the investigator must obtain documented approval from Lilly or its designee to allow the inadvertently enrolled patient to continue in the study with or without treatment with investigational product.

Safety follow-up- is required as outlined in Section 2 (Schedule of Activities), Section 9.2 (Adverse Events), and Section 9.4 (Safety) of the protocol.

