## 6.3. Use of an “Efficacy Subset” of Patients

**Entered population** set includes those patients who sign the informed consent form directly or through their legally acceptable representatives.

**Enrolled population** set includes all patients who have entered the study and who are not considered screen fails at or before Visit 6 (i.e. patients not excluded due to not meeting inclusion criteria or meeting exclusion criteria during screening/pre-treatment period).

**Efficacy population** set includes all enrolled patients who have at least one dose of baricitinib.

**Safety population** set includes all enrolled patients who receive at least 1 dose of baricitinib and who did not discontinue the study for the reason “Lost to Follow-up” at the first postbaseline visit (Visit 7).

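### Protocol 10.2 limits its analysis sets to patients who meet every eligibility criterion, yet some who fail one can be dosed; SAP 6.3 would keep them, so the two documents conflict

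*Protocol*

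**What the plan says.** Protocol 10.2 defines two sets. Enrolled is "All subjects who sign informed consent or assent (as applicable), and meet all eligibility criteria". The Full Analysis Set is "All enrolled subjects who take at least 1 dose of study treatment". The protocol defines no separate safety set.

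Two provisions let a patient who fails a criterion receive drug:

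- Protocol 6.1, criterion [3], sets a minimum diary score and then adds an exception: "If the average daily diary score does not meet the criterion" but the patient's condition justifies assessment in the study, "moving to Visit 6 may be allowed after consultation with Lilly or its designee". The sponsor or its designee makes the decision. The initial dose is prescribed at Visit 6.
- Protocol 8.1.3 covers a patient who "did not meet enrollment criteria and was inadvertently enrolled". Treatment stops by default, but with documented sponsor approval the site may "allow the inadvertently enrolled patient to continue in the study with or without treatment with investigational product".

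The opening of Protocol Section 6 says that prospective approvals of violations of the entry criteria, "also known as protocol waivers or exemptions, are not permitted". The opening of Section 9 repeats the ban.

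SAP 6.3 uses a different rule. Its Enrolled population is the patients who entered the study and "who are not considered screen fails at or before Visit 6". Its Efficacy population is the enrolled patients with at least one dose. Its Safety population is the same, less any patient lost to follow-up at Visit 7.

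**The concern.** An analysis set should not depend on a condition that the protocol itself allows to fail in a treated patient. Here the condition is full eligibility, and the set that inherits it is the only dosed set the protocol defines. A patient dosed under 8.1.3, or on a literal reading under criterion [3], has efficacy and safety data that belong to no protocol set, while the SAP would count that patient.

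Two things are at stake. First, with about 5 patients planned and results summarised by disease, keeping or dropping one patient can change a disease's result, and the documents disagree on which to do. Second, a patient admitted below the diary score differs from the others in a way that affects the efficacy summaries, and nothing in the plan singles that patient out.

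**Working it through.** The plan gives no figure to reproduce: sample size is set by rarity and no formal analysis is planned. The check compares definitions.

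**Step 1. Where each dosed patient falls.**

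| Dosed patient | Protocol Enrolled and Full Analysis Set | SAP Enrolled and Efficacy |
|---|---|---|
| Meets all criteria | in | in |
| Admitted below the diary score under [3] | out on a literal reading; in if the exception counts as meeting the criterion | in |
| Found ineligible after dosing (8.1.3), continued or stopped | out | in |

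The SAP column follows because Protocol 6.4 reserves the term screen failure for patients never assigned to study treatment, so a dosed patient is not one. The third row has no alternative reading. Section 8.1.3 itself calls that patient enrolled, which 10.2 would not, and requires safety follow-up for which the protocol has no analysis set.

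**Step 2. Entry score against response threshold** (Protocol 6.1 [3]; SAP Table JAJE.3, full mean diary score).

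| Disease | Entry score | Response threshold |
|---|---|---|
| NNS/CANDLE | ≥0.5 | <0.5 |
| SAVI | ≥1.0 | <1.0 (also <0.5) |
| AGS | ≥0.5 | <0.5 |

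For each disease the entry score is the complement of a response threshold. A patient below the entry score at Visit 6 therefore meets that threshold before the first dose. This does not follow for an NNS/CANDLE patient who was below the score only at Visit 2, for the SAVI <0.5 threshold, or for the thresholds that leave out respiratory or neurological symptoms.

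Scores cannot fall below 0, so this patient's improvement must be smaller than 0.5 (NNS/CANDLE, AGS) or 1.0 (SAVI).

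**Step 3. Size within a disease.** One patient carries weight 1/n in a disease mean:

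- n = 1: 1/1 = 100%
- n = 2: 1/2 = 50%
- n = 3: 1/3 = 33%

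These group sizes are assumed. For n = 2, with changes d1 (regular entrant) and d2 (below-score entrant), the mean is (d1 + d2)/2 with the patient and d1 without. The shift is (d1 + d2)/2 − d1 = (d2 − d1)/2. If the below-score entrant stays below the threshold and the other patient does not respond, the responder percentage is 1/2 = 50% with the patient and 0/1 = 0% without. Keeping the patient can therefore raise the responder percentage while making the mean change smaller.

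**Step 4. How likely.** The documents give no rate. If each of 5 patients independently had an assumed chance p of entering by one of these routes, the chance of at least one is 1 − (1 − p)^5: 22.6% for p = 5%, 41.0% for 10%, 67.2% for 20% and 83.2% for 30%. This range shows only how far the answer depends on an unknown p.

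**The case against.** The strongest reply is that the SAP governs the analysis. Its safety section names the SAP Safety population, and the Efficacy population of SAP 6.3 is evidently meant for the efficacy summaries. Protocol 10.3.3 and 10.3.4 never invoke the Full Analysis Set. SAP 6.1 also says that changes from the protocol's analysis methods will be explained in the study report. This largely stands: the patient would probably be analysed. It does not correct the protocol's rule, and the SAP revision history does not mention the difference.

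Second, the exception is printed inside criterion [3] and framed as an eligibility decision, so a patient admitted under it could count as eligible. The laboratory note in exclusion [22] has the same structure. This reading is tenable, although the text of [3] itself says that the score does not meet the criterion. It cannot cover 8.1.3.

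Third, SAP 6.14 already names incorrectly enrolled patients as a possible important deviation, promises a listing of all important deviations, and refers to a Trial Issue Management Plan that says whether an additional analysis leaves them out. That covers much of the 8.1.3 case. It does not clearly cover a patient admitted under [3] with permission, who may never be logged as a deviation. The planned by-visit diary listings would let a careful reader find such a patient, but only by looking.

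**Conclusion.** The conflict is real and is one of definition, not of calculation. It is certain for a dosed patient under 8.1.3 and depends on the reading for a patient under criterion [3]. One affected patient would be 50% of a disease group of 2, a group size that is assumed. The documents do not show that any such patient exists.

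A reader might infer four stronger things that the documents do not support:

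- **That a treated patient's safety data will be lost.** This would happen only if the protocol definition were applied in place of the SAP's.
- **That open-label results could steer who is admitted under [3].** That decision comes before the first dose, when no on-treatment result exists. Selective exclusion is conceivable only for ineligibility found after dosing, and again only under the protocol definition.
- **That [3] flatly contradicts the no-waiver statements.** Using an allowance written into the protocol is not clearly a violation of it. The text is ambiguous and needs clarifying.
- **That 20% of the primary result is at risk.** One of 5 is 20% of the planned patients, but the primary change is summarised by disease, so this is not a share of any planned primary mean.

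**What to change.** 1. In Protocol 10.2 and SAP 6.3, define the full analysis/efficacy set and the safety set as all patients who take at least one dose, regardless of eligibility deviations, and use the same set names in both. If an Enrolled set tied to eligibility is kept, do not build the dosed sets on it. The same wording removes the SAP Safety population's exclusion of dosed patients lost to follow-up at Visit 7.
2. In the listings, flag every patient admitted below the diary score, stating the visit concerned, and every patient found ineligible after enrolment.
3. Show the by-disease primary change and responder percentage with and without flagged patients. Where the flagged patient is the only one with that disease, the flag is enough.
4. Clarify how the criterion [3] exception fits the no-waiver statements in Sections 6 and 9. This point takes no view on what the entry rule should be.

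The cost is a few definitions, one flag and one small display, with no new data. The SAP efficacy set should not change; the safety set could gain a patient. SAP Version 5 is to be approved before final database lock, so the wording can still be corrected. Version 4 was approved after the 52-week lock, so the study report should state that the alignment came after those data. A set that takes in every dosed patient leaves no room for selection.
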